## 16.6. Efficacy Analysis

Efficacy analyses will be performed on the FAS, which include the Safety Set subset with a baseline and at least 1 postbaseline LDH measurement.

Absolute LDH levels, and the change and percent change from baseline will be summarized at all study visits. Baseline is defined as the average of all available assessments on or prior to the first ALXN1210 infusion. A mixed model for repeated measures (MMRM) with the fixed, categorical effect of visit and fixed, continuous effect of baseline LDH levels as covariates will be fit to test whether changes and percent changes differ from zero at each time point. An unstructured covariance analysis will be used to model the within-patient errors. If this analysis fails to converge, the following structures will be tested and the final covariance structure will be determined by Akaike's information criterion: first-order autoregressive, compound symmetry, and Toeplitz method. The Kenward-Roger approximation will be used to estimate denominator degrees of freedom. As a sensitivity analysis, changes and percent changes from baseline will be analyzed, using the Wilcoxon signed-rank test. Graphical displays will be presented, as appropriate.

The percentage of patients with clinical symptoms will be summarized for all study visits.

Changes in hematologic measures will be similarly analyzed using an MMRM and Wilcoxon signed-rank test.

Scoring guidelines for the FACIT-Fatigue and EORTC scales will be used to calculate QoL scores. Changes from baseline in FACIT-Fatigue and EORTC scale scores will be summarized descriptively for all study visits, and analyzed using MMRM and Wilcoxon signed rank test.

Transfusion rates and the incidence rate of MAVEs will be summarized.

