4.1. Changes from Analyses Specified in the Protocol

There are no changes from analyses specified in the protocol apart from the inclusion of data up to the Day 281 visit for Cohort 4 (the first dose in the Extension Period) in the analyses.

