7.2.1. Primary Analysis

The primary efficacy endpoint is the change from baseline in lactate dehydrogenase (LDH) levels to Day 253. Absolute LDH levels, and the change and percent change from baseline will be summarized at all study visits, by cohort and overall. Baseline is defined as the average of all available assessments prior to first ALXN1210 infusion.

A mixed model for repeated measures (MMRM) (Mallinckrodt, 2001; Mallinckrodt, 2004) with the fixed, categorical effect of visit and fixed, continuous effect of baseline LDH levels as covariates will be fit to test whether changes and percent changes differ from zero at each time point for the combined cohorts. An unstructured covariance matrix will be used to model the within-patient errors. If this analysis fails to converge, the following structures will be tested, and the final covariance structure will be determined by Akaike's information criterion: first order autoregressive, compound symmetry, and Toeplitz method. The Kenward-Roger approximation will be used to estimate denominator degrees of freedom. Confidence intervals (CI) and p-values from the model will be presented.

As a sensitivity analysis, changes and percent changes from baseline will be analyzed using the Wilcoxon signed-rank test. Last observation carried forward (LOCF) will be used for patients with missing Day 253. If MMRM analysis fails to converge given the small sample size in this study, Wilcoxon signed-rank test will be used for the primary analysis of LDH.

The number (%) of patients achieving LDH levels at or below 1.0 times upper limit of normal (1.0 x ULN) and levels at or below 1.5 x ULN) will be displayed.

Mean (\pm 95% CI) of absolute LDH levels, and the change and percent change from baseline will be plotted over time, by cohort and overall.

By-patient data listings of LDH data will be produced.

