7.2.1.1. Handling of Dropouts or Missing Data

Missing data for primary, secondary and exploratory endpoints analyses will be handled as indicated for the specific analysis.

Missing data for QOL instruments will be handled as specified in the instructions for each instrument and as specified in Section 9.5 .

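### LOCF for missing Day 253 LDH, set beside a missing-at-random MMRM, leaves a return towards baseline after stopping drug untested

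*SAP*

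**What the plan says.** SAP 7.2.1 makes an MMRM on the combined cohorts the primary analysis of change and percent change in LDH, tested against zero. It specifies no imputation for that model. Three further statements in the section matter here.

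- On the unstructured covariance matrix: "If this analysis fails to converge, the following structures will be tested, and the final covariance structure will be determined by Akaike's information criterion". The structures listed are first-order autoregressive, compound symmetry and Toeplitz.
- On sensitivity: "As a sensitivity analysis, changes and percent changes from baseline will be analyzed using the Wilcoxon signed-rank test", followed directly by "Last observation carried forward (LOCF) will be used for patients with missing Day 253".
- Then: "If MMRM analysis fails to converge given the small sample size in this study, Wilcoxon signed-rank test will be used for the primary analysis".

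SAP 7.2.1.1 adds no rule of its own for LDH: "Missing data for primary, secondary and exploratory endpoints analyses will be handled as indicated for the specific analysis". SAP 7.2.2 repeats the Wilcoxon test with LOCF for the hemolysis-related hematologic parameters.

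Protocol 16.6 has the Wilcoxon test as a sensitivity analysis only ("As a sensitivity analysis, changes and percent changes from baseline will be analyzed, using the Wilcoxon signed-rank test"), with neither LOCF nor a switch to primary. SAP 4.1 does not list either addition: "There are no changes from analyses specified in the protocol apart from the inclusion of data up to the Day 281 visit for Cohort 4".

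Protocol 8.3 encourages patients withdrawn from ALXN1210 to keep attending until they start another complement-targeted therapy, and places the Early Termination visit before that therapy begins.

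**The concern.** The trial has one treatment arm per cohort and no control, and the test is of change against zero. A favourable handling of missing values therefore has no comparator to offset it. If a responding patient stops drug and leaves, the last LDH may be low because drug was still active. LOCF places that value at Day 253. The MMRM, under missing at random, also predicts the missing value from the patient's observed course and from patients who stayed.

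A sensitivity analysis earns its place by relaxing the assumption most in doubt. Here that assumption is that benefit persists after stopping, and both analyses keep it for such patients. At stake is the credibility of the estimated LDH reduction more than its significance.

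**Working it through.** **Inputs.** Mean change -40%, SD 45%, n = 20, two-sided paired t-test at 5%, 15% dropout, up to 26 enrolled (SAP 9.3; Protocol 16.3). Half-life about 43 days (Protocol 6.2). LDH visits from Protocol Tables 4 to 7. Off-drug LDH is not in the documents, so two values are assumed: -20% (half return) and 0% (full return).

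**1. The plan's own figure.** Noncentrality = (40/45) × √20 = 3.98 on 19 df. Exact power is 96.5%, which agrees with the stated value of approximately 95%.

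**2. Patients missing.** 0.15 × 26 = 3.9, so about 4 of 26; 0.15 × 20 = 3 of 20.

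**3. Shift in the mean.** Suppose m of N patients lack Day 253 and had the average on-drug response. LOCF keeps the mean at -40%. With assumed off-drug value c, the mean is [(N - m)(-40) + m·c]/N.

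| m of N | c | Mean | Overstatement by LOCF |
|---|---|---|---|
| 4 of 26 | -20 | (22 × -40 + 4 × -20)/26 = -36.9% | 3.1 points |
| 4 of 26 | 0 | (22 × -40)/26 = -33.8% | 6.2 points |
| 3 of 20 | -20 | (17 × -40 + 3 × -20)/20 = -37.0% | 3.0 points |
| 3 of 20 | 0 | (17 × -40)/20 = -34.0% | 6.0 points |

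**4. Effect on the signed-rank test.** Simulated power, 4000 runs, normal changes with mean -40 and SD 45. Values for the missing patients are spread around the assumed off-drug mean with the same SD.

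| m of N | LOCF | Half return | Full return |
|---|---|---|---|
| 3 of 20 | 95-96% | 92% | 86% |
| 4 of 26 | 99% | 97% | 94% |

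If exact zeros are imputed instead, the standard signed-rank test discards them and power is close to that of completers: about 92-93% against 91-92% for 3 of 20, and about 97-98% for both for 4 of 26. Plain zero imputation is therefore not a real stress test in this procedure.

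**5. Could the carried value be an on-drug value?** Fraction of drug remaining after t days = 0.5^(t/43): 26% at 84 days and 7% at 168 days. A value taken at or soon after stopping may reflect an effect that is largely gone by Day 253.

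**6. Route to the primary analysis.** LDH is scheduled at 15 post-baseline visits from Day 7 to Day 253. Unstructured covariance needs 15 × 16/2 = 120 parameters from at most 26 patients, so failure at that step is plausible. The alternatives need 2 (autoregressive), 2 (compound symmetry) and 15 (Toeplitz). Failure of all of them is unlikely.

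**The case against.** The strongest reply has four parts.

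- **LOCF is confined to a sensitivity analysis.** This stands. The MMRM estimates and confidence intervals involve no imputation, so the 3 to 6 points are a shift in a LOCF mean, not in the primary estimate. A reader might infer from the 120 parameters that LOCF is likely to become primary. The documents do not support that, because three simpler structures are also provided. What remains is that the SAP attaches two consequences to non-convergence (other structures, or the Wilcoxon test) without ordering them.
- **The direction of bias is not given.** This stands in part. A reader might infer that both analyses are certainly biased in the drug's favour. The documents do not say why patients would leave. One who leaves for lack of effect carries a high LDH forward. The favourable direction applies to patients who stop while responding.
- **Off-drug values are already used.** This stands. LOCF applies only when Day 253 is missing, nothing excludes LDH taken after stopping, and Protocol 8.3 encourages attendance. The gap concerns those who leave or switch therapy.
- **Missing does not mean off drug.** This stands. A patient still on drug may miss the visit or have a sample cancelled centrally (Protocol 14.1.6). Assigning baseline LDH to that patient would be an error the other way.

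None of this supplies an analysis in which benefit is lost after stopping.

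**Conclusion.** The point holds as a gap in the sensitivity analyses, and it should be closed. LOCF ignores the reason for missingness, the MMRM assumes missing at random, and no planned analysis tests a return towards baseline. Agreement between the two therefore says little about that risk.

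The size is modest: about 3 points (half return) to 6 points (full return) on a planned -40%. This assumes that all of the 15% dropouts stopped drug, lack Day 253 and had the average on-drug response. The upper figure is a bound under those assumptions. The gap scales with the on-drug fall, so larger numbers are tempting, but the plan's only effect figure is -40%.

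A reader might also infer that significance is at risk. The calculations do not show that: simulated power is still 86% to 94% in the full-return case. The matter bears on the estimate far more than on the test against zero.

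**What to change.** 1. State that observed Day 253 LDH is used whether or not the patient is still on drug.
2. For patients who discontinued ALXN1210 and have no Day 253 value, report beside LOCF an analysis assuming return to baseline. Give the mean change with its CI, since that shows the shift directly. Accompany it with a signed-rank test that keeps zeros in the ranking (Pratt) or, as a firmer stress test, one that draws the imputed values around baseline.
3. Do not impute baseline for patients still on drug who missed the visit or had a cancelled sample.
4. State that the Wilcoxon test becomes primary only after every listed covariance structure has failed.
5. Apply items 1 to 3 in SAP 7.2.2, and list the LOCF rule and the Wilcoxon fallback in SAP 4.1 as additions to the protocol's analysis.

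The cost is SAP wording, one extra run and a slightly less favourable sensitivity estimate. If the Day 253 report already exists, the added analysis should be labelled post hoc.

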7.2.1.1. Handling of Dropouts or Missing Data

Missing data for primary, secondary and exploratory endpoints analyses will be handled as indicated for the specific analysis.

Missing data for QOL instruments will be handled as specified in the instructions for each instrument and as specified in Section 9.5 .

7.2.1.2. Subgroup Analysis

Summaries will be presented as indicated for the specific analysis by cohort. No other subgroup analyses are planned due to the small sample size.

7.2.1.3. Multicenter Studies

This is a multicenter study; however, the expected sample size is not sufficient to perform any meaningful efficacy summaries by center.

7.2.1.4. Hypothesis Testing and Significance Level

Hypothesis testing for the change and percent change in LDH from baseline to Day 253 will be two-sided and performed at the 0.05 level of significance. For all the other parameters, p-values will be provided descriptively. Estimates of treatment effect on efficacy parameters will be accompanied by two-sided 95% confidence intervals, as indicated for the specific analysis.

7.2.1.5. Sensitivity Analyses

Sensitivity analyses for the primary efficacy endpoint, LDH, are presented in Section 7.2.1. Sensitivity analyses for the secondary efficacy endpoints are presented in Section 7.2.2.

7.2.2. Secondary Analyses

Descriptive statistics for the secondary endpoints of absolute, changes and percentage changes from baseline in hemolysis-related hematologic parameters (free hemoglobin, haptoglobin, reticulocyte count, PNH red blood cell (RBC) clone, and D-dimer) will be produced for each visit, by cohort and overall. Baseline is defined as the last non-missing assessment value prior to the first ALXN1210 infusion. For any hemolysis-related hematologic parameter with a result value below or above the limit of quantification (i.e., a result of $<x$ or $>x$) the numeric result without the $<$ or $>$ symbol will be used in the analyses. The changes and percentage changes from baseline in hemolysis-related hematologic parameters will be analyzed in the same manner as described for the primary efficacy endpoint utilizing the MMRM approach.

As a sensitivity analysis, changes and percent changes from baseline will be analyzed using the Wilcoxon signed-rank test. Last observation carried forward (LOCF) will be used for patients with missing Day 253.

Individual patient plots of the hemolysis-related parameters will be produced. The following figures will also be produced by cohort and overall:

- Mean ($\pm 95\%$ CI) endpoint values over time
- Mean change/percentage change ($\pm 95\%$ CI) from baseline in endpoint values over time

Shift tables will be produced for all study visits by cohort and overall for the following clinical manifestations of PNH: fatigue, abdominal pain, dyspnea, dysphagia, chest pain, and erectile dysfunction.

By-patient data listings containing all secondary endpoints will be produced.

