5.1.2. Secondary Endpoints

The secondary efficacy endpoints include:

- Changes in hemolysis-related hematologic parameters: free hemoglobin, haptoglobin, reticulocyte count, PNH red blood cell (RBC) clone, and D-dimer.
- Changes in clinical manifestations of PNH: fatigue, abdominal pain, dyspnea, dysphagia, chest pain, and erectile dysfunction.

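### SAP 7.2.2 analyses results beyond the limit of quantification as equal to the limit, which pulls change in hemolysis parameters toward zero and ties percent change to the assay

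*SAP*

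**What the plan says.** SAP 5.1.2 lists the secondary laboratory endpoints: "Changes in hemolysis-related hematologic parameters: free hemoglobin, haptoglobin, reticulocyte count, PNH red blood cell (RBC) clone, and D-dimer". SAP 7.2.2 sets the rule for results reported with a < or > sign: "For any hemolysis-related hematologic parameter with a result value below or above the limit of quantification", "the numeric result without the $<$ or $>$ symbol will be used in the analyses". The rule has no exception by parameter, by visit or by direction of the limit.

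The substituted values are used throughout SAP 7.2.2:

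- Descriptive statistics and mean plots of the value, the change and the percent change.
- A repeated-measures model of change and percent change, which "will be analyzed in the same manner as described for the primary efficacy endpoint utilizing the MMRM approach". The primary model in SAP 7.2.1 has visit and a "fixed, continuous effect of baseline LDH levels as covariates will be fit to test whether changes and percent changes differ from zero".
- A Wilcoxon signed-rank test of change and percent change, as the sensitivity analysis.

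Baseline is a single value: "Baseline is defined as the last non-missing assessment value prior to the first ALXN1210 infusion". SAP 9.4 makes that value the denominator of percent change. SAP 7.2.1.4 makes p-values for everything except LDH descriptive. Protocol 16.6 gives no rule of its own for such results. Neither document plans a count of results beyond the limit or an analysis that treats them as censored.

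**The concern.** A result of '<x' says only that the true value lies somewhere below x. Entering x treats it as known. A patient below the limit at both visits gets a change of exactly zero. A patient below the limit at baseline and above it later gets a percent change whose denominator is a property of the assay.

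This matters where results collect at a limit. Protocol 8.1 requires a mean screening LDH of at least 3 times the upper limit of normal, so all patients enter with active hemolysis. It is plausible that haptoglobin is then at or below its limit at baseline in a good share of them, but the documents do not say so. The same rule acts after treatment on parameters expected to fall.

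At stake are the reported size of change and its confidence interval. These are the main product of a descriptive secondary analysis, and a reader could not tell a small effect from an assay floor.

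**Working it through.** **1. The plan's own figure.** Neither document gives a figure for these parameters. The only stated one is the power for LDH (SAP 9.3): n = 20, mean -40%, SD 45%, two-sided paired t-test at 5%. The noncentrality is (40/45) x sqrt(20) = 3.98 and the critical t on 19 df is 2.09, giving 96.5%, consistent with the stated approximate 95%. The limit rule does not enter this calculation.

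**2. What the rule does to one patient (no assumptions).** Let L be the lower limit, the baseline be below L, and the later value be Y.

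- Y above L: analysed change = Y - L; analysed percent change = 100(Y - L)/L, whatever the true baseline. With L = 1 and Y = 2 the plan always gives +1 and +100%. The true values are +1.9 and +1900% if the baseline is 0.1, or +1.5 and +300% if it is 0.5.
- Y below L: analysed change = 0.

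The error in absolute change is at most L. The error in percent change has no bound. Clipping values at a limit never reverses a patient's change and never enlarges it, in difference or in ratio. So when patients move mainly in one direction, the mean moves toward zero.

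**3. Size for a rise (assumed inputs).** Values are lognormal with L = 1 and log-SDs of 0.8 between and 0.4 within patients, so the total log-variance is 0.64 + 0.16 = 0.80 and s = 0.894. Baseline medians m of 1, 0.5 and 0.25 put Phi(-ln m / s) = 50%, 78% and 94% of baselines below the limit. The median doubles.

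- True mean percent change: the log-ratio has variance 2 x 0.16 = 0.32, so the mean ratio is 2 x exp(0.16) = 2.35, or +135%. It exceeds +100% because ratios are skewed.
- True mean: m x exp(0.40) = 1.492m.
- Mean after substitution: Phi(-ln m / s) + 1.492m x Phi((ln m + 0.80)/s). For m = 2, 1, 0.5 and 0.25 this is 3.061, 1.715, 1.189 and 1.035.

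Mean percent change after substitution and the share of zero pairs are from simulation.

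| Baselines below limit | Mean % change, true | As planned | Mean change, true | As planned | Shortfall | Pairs set to zero |
|---|---|---|---|---|---|---|
| 50% | +135% | +79% | 1.492 | 1.346 | 9.8% | 21% |
| 78% | +135% | +40% | 0.746 | 0.526 | 29.5% | 49% |
| 94% | +135% | +14% | 0.373 | 0.154 | 58.6% | 77% |

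**4. Size for a fall (same assumptions, baseline median 3).** A median fall of 67% (to 1) has a true mean percent change of exp(0.16)/3 - 1 = -61% and reads -47%; mean change is -2.79 instead of -2.98 (6% short). A median fall of 92% (to 0.25) has exp(0.16)/12 - 1 = -90% and reads -57%; mean change is -3.48 instead of -4.10 (15% short).

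**5. The sensitivity analysis.** The Wilcoxon test takes the same substituted values. It keeps the direction of pairs that cross the limit, but pairs below the limit at both visits enter as zeros. Its agreement with the MMRM therefore says nothing about the substitution.

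**6. The baseline covariate.** SAP 7.2.1 names baseline LDH; reading it as each parameter's own baseline follows from the instruction to analyse in the same manner, but is not spelled out. If a share q of baselines is at the limit, all n are equal with probability q^n. For n = 24 that is 0.78^24 = 0.3% and 0.94^24 = 23%. A constant covariate is aliased with the intercept: in a three-visit check the design matrix had rank 3 with and without it, and fitted visit means were identical.

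**The case against.** The case for leaving the plan alone has several parts.

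- **No frequency is given.** The documents state no assay limit and no share of results beyond it. That haptoglobin is often at its limit here is an assumption, not a fact from the plan. This stands, and is why the size is shown as a range.
- **Absolute change is affected much less than percent change.** At 50% below the limit the shortfall is about 10%, and per patient it cannot exceed the limit. This stands; the heavier distortion needs percent change, or most values below the limit at both visits.
- **The consequence is limited.** P-values are descriptive, the primary LDH analysis is untouched, and individual plots and by-patient listings of these parameters are planned. This stands. Plots and listings do not correct the summary estimates, however.
- **A censored mixed model is fragile here.** With 20 to 26 patients and many visits, SAP 7.2.1 already foresees that even the ordinary MMRM may not converge. With most baselines censored, the result would rest largely on the assumed distribution. This is a sound reason to keep the MMRM.

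Two stronger readings are tempting. A reader might infer that the model cannot be fitted if all baselines equal the limit. Step 6 shows that only the covariate becomes redundant; change by visit is still estimated. Near-constancy is the more awkward case, because the few patients above the limit then set the slope. A reader might also infer false precision from the reduced spread. That is not shown: for the three doubling settings the ratio of mean to SD of absolute change falls from 0.63 to about 0.56, 0.44 and 0.28, so tests lose sensitivity. With no true shift, absolute change shows no bias.

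**Conclusion.** The point holds as a cheap improvement. The rule is explicit, nothing in either document softens it, and its direction is clear: where many results lie beyond a limit, change is understated and percent change partly measures the assay.

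The size depends on a share that the documents do not give. Steps 3 and 4 show a range from modest (about 6% to 10% of absolute change) to severe (a mean of +14% for a true +135%). It rests on lognormal values, the two assumed log-SDs and the chosen medians. A parameter with few results beyond its limit would be almost unaffected.

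The documents do not support a claim that the trial could show a benefit that is not there, or that the primary conclusion is at risk. The rule tends to understate benefit, in descriptive secondary endpoints only.

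**What to change.** In SAP 7.2.2, for each hemolysis-related parameter with results beyond a limit:

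1. Report n (%) beyond the limit at each visit, by cohort and overall.
2. Compare the share of quantifiable results at baseline and at Day 253 by exact McNemar test, with the p-value descriptive as for the other secondary analyses.
3. Flag percent change as not interpretable where the baseline is below the limit.
4. Where such results are common, base the conclusion on the counts and the rank test of change, not on the mean percent change.
5. Keep the MMRM as planned. Add a censored-data (Tobit-type) analysis of the change at Day 253 as a sensitivity analysis where it can be fitted. For example, a baseline below L with a later value Y enters as a change between Y - L and Y.
6. State that the covariate is the parameter's own baseline, and that it is omitted if constant.

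The cost is SAP wording and a little more programming, with no new data, visits or patients. The censored analysis needs a distributional assumption and may not be estimable when nearly all baselines are below the limit; the counts and the McNemar comparison do not have that weakness.
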